8.2 Treatment Overdose

There is no known antidote for an overdose of either LGX818, MEK162 or LEE011. Supportive measures should be instituted.

In the event of an overdose, the investigator/treating physician should:

1. Contact the medical monitor within 24 hours.
2. Closely monitor the patient for any AEs/SAEs and laboratory abnormalities for at least 5 half-lives or 28 calendar days after the overdose of study treatment (whichever is longer). Closely monitor the patient for any AEs/SAEs.
3. Document the quantity of the excess dose as well as the duration of the overdose in the CRF.
4. Overdose is reportable to Safety **only when associated with an SAE**.

Decisions regarding dose interruptions or modifications will be made by the Investigator in consultation with the Sponsor Medical Monitor based on the clinical evaluation of the patient.

8.3 Warnings and precautions

No evidence available at the time of the approval of this study protocol indicated that special warnings or precautions were appropriate, other than those noted in the provided Investigator Brochure. Additional safety information collected between IB updates will be communicated in the form of Investigator Notifications. This information will be included in the patient informed consent and should be discussed with the patient during the study as needed.

8.4 Data Monitoring Committee

A Data Monitoring Committee (DMC) will not be in place for this trial. Instead, the Sponsor will convene a joint teleconference with the participating Investigators of the dose escalation at the end of each treatment cohort. At the dose escalation teleconference the clinical course (available safety information including both DLTs and all \geq CTCAE Grade 2 toxicity data during Cycle 1, PK and PD data as appropriate) for each patient in the current dose cohort will be described in detail. Updated safety data on other ongoing patients, including data in later cycles, will be discussed as well.

Dose escalation decisions will be based on a clinical synthesis of all relevant available data and not solely on DLT information. Selection of the actual dose for the next cohort of patients will be guided by the BLRM (with EWOC) recommendation, and a medical review of available relevant clinical, PK, PD and laboratory data. The parties i.e. study Investigators and the Sponsor, must reach a consensus on whether to declare MTD, escalate the dose any further, or whether to de-escalate and/or expand recruitment into particular cohorts. The Sponsor will prepare minutes from these meetings and circulate them to all concerned ([Section 6.2.4.2.1](#)).

9 Data collection and management

9.1 Data confidentiality

Information about study subjects will be kept confidential and managed under the applicable laws and regulations. Those regulations require a signed subject authorization informing the subject of the following:

- What protected health information (PHI) will be collected from subjects in this study
- Who will have access to that information and why
- Who will use or disclose that information
- The rights of a research subject to revoke their authorization for use of their PHI.

In the event that a subject revokes authorization to collect or use PHI, the investigator, by regulation, retains the ability to use all information collected prior to the revocation of subject authorization. For subjects that have revoked authorization to collect or use PHI, attempts should be made to obtain permission to collect at least vital status (i.e. that the subject is alive) at the end of their scheduled study period.

The data collection system for this study uses built-in security features to encrypt all data for transmission in both directions, preventing unauthorized access to confidential participant information. Access to the system will be controlled by a sequence of individually assigned user identification codes and passwords, made available only to authorized personnel who have completed prerequisite training.

9.2 Site monitoring

Before study initiation, at a site initiation visit or at an investigator's meeting, Sponsor personnel (or designated CRO) will review the protocol and eCRFs with the investigators and their staff. During the study, the field monitor will visit the site regularly to check the completeness of patient records, the accuracy of entries on the eCRFs, the adherence to the protocol to Good Clinical Practice, the progress of enrollment, and to ensure that study treatment is being stored, dispensed, and accounted for according to specifications. Key study personnel must be available to assist the field monitor during these visits.

The investigator must maintain source documents for each patient in the study, consisting of case and visit notes (hospital or clinic medical records) containing demographic and medical information, laboratory data, electrocardiograms, and the results of any other tests or assessments. All information recorded on eCRFs must be traceable to source documents in the patient's file. The investigator must also keep the original signed informed consent form (a signed copy is given to the patient).

The investigator must give the monitor access to all relevant source documents to confirm their consistency with the eCRF entries. The Sponsor's monitoring standards require full verification for the presence of informed consent, adherence to the inclusion/exclusion criteria and documentation of SAEs. Additional checks of the consistency of the source data with the eCRFs are performed according to the study-specific monitoring plan.

9.3 Data collection

The designated investigator staff will enter the data required by the protocol into the Electronic Case Report Forms (eCRF). The eCRFs have been built using fully validated secure web-enabled software that conforms to 21 CFR Part 11 requirements, Investigator site staff will not be given access to the EDC system until they have been trained. Automatic validation programs check for data discrepancies in the eCRFs and allow modification or verification of the entered data by the investigator staff.

The Principal Investigator is responsible for assuring that the data entered into eCRF is complete, accurate, and that entry and updates are performed in a timely manner.

PK and biomarker (blood and tissue) samples drawn during the course of the study will be collected from the Investigator sites and analyzed by a Sponsor-assigned laboratory or contracted central labs. ECG data (except the screening/baseline ECG) collected during the study will be reviewed and processed centrally by a specialist CRO. Designated investigational site staff will enter the information required by the protocol into the appropriate eCRF (and/or designated laboratory requisition forms that are printed on 2 or 3-part, non-carbon-required paper). Field monitors will review the eCRFs and laboratory paper requisition forms for accuracy and completeness and instruct site personnel to make any required corrections or

additions. One copy of the requisition form will be forwarded to each analytical laboratory with the respective sample(s) by the field monitor or by the designated investigational site staff; and one copy will be retained at the investigational site.

9.4 Database management and quality control

Sponsor personnel (or designated CRO) will review the data entered by investigational staff for completeness and accuracy. Electronic data queries stating the nature of the problem and requesting clarification will be created for discrepancies and missing values and sent to the investigational site via the EDC system. Designated investigator site staff are required to respond promptly to queries and to make any necessary changes to the data.

Concomitant treatments entered into the database will be coded using the WHO Drug Reference List, which employs the Anatomical Therapeutic Chemical classification system. Medical history/current medical conditions and adverse events will be coded using the Medical dictionary for regulatory activities (MedDRA) terminology.

Biomarker and PK samples and ECG (except screening/baseline) will be processed centrally, and the results for these will be sent electronically to the Sponsor (or a designated CRO).

After database lock, the investigator will receive a CD-ROM or paper copies of the patient data for archiving at the investigational site.

10 Statistical methods and data analysis

[Any language regarding the triple combination of LGX818/MEK162/LEE011 in this Section is not applicable to the USA and Singapore]

Data will be analyzed by the Sponsor and/or designated CRO. Any data analysis carried out independently by the investigator must be submitted to the Sponsor before publication or presentation.

It is planned that the data from participating centers in this protocol will be combined, so that an adequate number of patients will be available for analysis. Data will be summarized with respect to demographic and baseline characteristics, efficacy and safety observations and measurements and all relevant PK and PD measurements.

Categorical data will be presented as frequencies and percentages. For continuous data, mean, standard deviation, median, 25th and 75th percentiles, minimum, and maximum will be presented.

An initial clinical study report (CSR) will be presented based on the Ph Ib/II patients' data from the dual study drug combination. The cut-off for reporting will be either LPFV + 18 months or when 80% of the patients treated with the dual study drug combination can be assessed for PFS, whichever occurs first.

Additional data for any patients continuing to receive the LGX818 and MEK162 dual combination past the cut off point for the initial reporting, as allowed by the protocol, and the Phase Ib/II patients' data from the LGX818 and MEK162 and LEE011 triple combination will be summarized in a final CSR that will be prepared when all patients have completed or discontinued from the study.

The following rules will be followed for reporting results unless stated otherwise:

- **Phase Ib dose escalation data:** Cohorts of patients treated with the same dose combination and regimen during the dose escalation part will be pooled into a common treatment group. All summaries, listings, figures and analyses will be displayed / performed by treatment group unless otherwise specified.
- **Phase II data:** Data will be summarized and listed by study arm.

Screen failure patients are those who signed the informed consent, but never started the study treatment for any reason. For these patients, the eCRF data collected, [Section 7.1.2.2](#), will not be included in any analysis, but will be reported in the CSR as separate listings.

10.1 Analysis sets

10.1.1 Full Analysis Set

The FAS includes all patients who received at least one dose of LGX818 or MEK162 or LEE011. Patients will be classified according to the planned treatment regimen (dose, schedule, tablet variant). The FAS will be used for all listings of raw data. Unless otherwise specified the FAS will be the default analysis set used for all analyses.

10.1.2 Safety Set

The safety set includes all patients who received at least one dose of LGX818 or MEK162 or LEE011, and have at least one valid post-baseline safety assessment. The statement that a patient had no AEs (on the AE eCRF) constitutes a valid safety assessment.

Patients will be classified according to treatment received, where treatment received is defined as:

- The treatment assigned if it was received at least once, or
- The first treatment received when starting therapy with study treatment if the assigned treatment was never received.

10.1.3 Dose-Determining Set

The dose-determining set (DDS) includes all patients from the safety set who either completed a minimum exposure requirement and have sufficient safety evaluations or discontinued prematurely due to a dose limiting toxicity (DLT).

A patient is considered to have met the minimum exposure requirement if having received at least 75% of the planned combination doses (i.e. 21 out of 28 planned daily doses for QD or BID, 11 out of 14 planned doses for an every other day dosing schedule, and 16 days out of 21 days for 3 week on, 1 week off dosing schedule) of study treatment within the first Cycle of dosing. The length of a cycle is 28 days.

Patients who do not experience DLT during the first cycle will be considered to have sufficient safety evaluations if they have been observed for ≥ 28 days following the first dose, and are considered by both the Sponsor and Investigators to have enough safety data to conclude that a DLT did not occur.

10.2 Patient demographics/other baseline characteristics

Demographic and other baseline data including disease characteristics will be summarized descriptively for all patients in the FAS.

10.3 Treatments (study treatment, concomitant therapies, compliance)

10.3.1 Study treatment

The actual dose and duration in days of LGX818 and MEK162 and LEE011 treatment as well as the dose intensity (computed as the ratio of actual dose received and actual duration) and the relative dose intensity (computed as the ratio of dose intensity and planned dose received/planned duration), will be listed and summarized by means of descriptive statistics. The summary data will be presented for each treatment cycle individually, as well as for all study days as a single category. The daily doses of LGX818, MEK162, and LEE011 for each patient will be summarized using descriptive statistics (e.g. mean, median, and modal doses). The FAS will be used. For patients who switch to the new MEK162 tablet variants, dose intensity will be calculated based on the bioavailability ratio between the original and new MEK162 tablet variants if the new and old variants are not similar. Details will be provided in report analysis plan (RAP).

10.3.2 Concomitant therapies

Concomitant medications and significant non-drug therapies prior to and after the start of the study drug treatment will be listed by patient and summarized by ATC (Anatomical therapeutic chemical classification system) term by means of contingency tables.

10.3.3 Compliance

Compliance to the protocol will be assessed by the number and proportion of patients with protocol deviations. These will be identified prior to database lock and will be listed and summarized.

10.4 Primary objective

Phase Ib

The primary purpose of the Phase Ib part of the study is to estimate the MTD(s) and/or RP2D(s) of the LGX818 and MEK162 dual combination and MTD(s) and/or RP2D(s) of LGX818 and MEK162 and LEE011 triple combination in patients with solid tumors harboring a BRAF V600 mutation (see [Section 3](#)). The corresponding method of analysis is an adaptive Bayesian logistic regression model (BLRM) guided by the escalation with overdose control (EWOC) principle ([Babb 1998](#)).

Phase II

The primary purpose of the Phase II part of the study is to assess the efficacy of the RP2D(s) of the dual combination of LGX818 and MEK162 combination in patients with metastatic BRAF

V600 mutant mCRC (arm 1), in patients with metastatic BRAF V600 mutant melanoma who have progressed after prior treatment with selective BRAF inhibitor (arm 2) and in patients with metastatic BRAF V600 mutant melanoma who are naïve to prior treatment with selective BRAF inhibitor (arm 3). The primary purpose of the Phase II part of triple combination of LGX818 and MEK162 and LEE011 is to assess the efficacy of the RP2D(s) in patients with metastatic BRAF V600 mutant melanoma who are naïve to prior treatment with selective BRAF inhibitor (arm A).

10.4.1 Variable

Phase Ib

Estimation of the MTD of the combination treatment will be based upon the estimation of the probability of DLT in Cycle 1 for patients in the dose-determining set. This probability is estimated by the model in Section 10.4.2. Note that more than one dose-combination of dual combination (LGX818 and MEK162) or triple combination (LGX818 and MEK162 and LEE011) may be identified as a MTD, and more than one RP2D may be established for further evaluation in the phase II part of the study.

The dose determining set (DDS) will be used for all dose determining analyses.

Phase II

Dual combination (LGX818 and MEK162)

For arm 1, the primary variable is the Disease Control Rate (DCR) at week 16. DCR is defined as the proportion of patients with a best overall response of complete response (CR), partial response (PR) or stable disease (SD). Estimation of the true DCR in this part of the study will be based upon observed DCR for patients in the FAS. The true DCR is estimated using a Bayesian design. The primary analysis of the DCR will be based on the local review of overall lesion responses.

For arms 2 and 3, the primary variable is the Objective Response Rate (ORR), defined as the proportion of patients with a best overall response of complete response (CR) or partial response (PR). Estimation of the true ORR in this part of the study will be based upon observed ORR for patients in the FAS. The true ORR is estimated using a Bayesian design. The Primary analysis of the ORR will be based on the local review of overall lesion responses.

Triple combination (LGX818 and MEK162 and LEE011)

For arm A, the primary variable is the Objective Response Rate (ORR), defined as the proportion of patients with a best overall response of complete response (CR) or partial response (PR). Estimation of the true ORR in this part of the study will be based upon observed ORR for patients in the FAS. The true ORR is estimated using a Bayesian design. The Primary analysis of the ORR will be based on the local review of overall lesion responses.

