7.2 Assessment types

7.2.1 Efficacy assessments

Tumor response will be evaluated locally by the investigator according to the guideline based on RECIST version 1.1 (see [Appendix 1](#)). Each subject will be evaluated for all potential sites of tumor lesions at Screening/baseline, at the end of Cycle 1 (not applicable for patients enrolled

in the Phase II part of the study) and Cycle 2 and then every 8 weeks (2 cycles) thereafter during the study treatment until disease progression. Screening/baseline imaging assessments may be performed within 21 days of treatment start, except whole-body bone scans, if applicable, which can be performed within 6 weeks of treatment start. On-study tumor assessments have a ± 7 day window, except for the tumor assessment on C1D28 which must be performed between week 3 and 4 after starting the study drug combination. Patients who have been on the LGX818/MEK162 dual- or triple-combination treatment for ≥ 24 months (Cycle 25 Day 1 onward) will be evaluated for all potential sites of tumor lesions every 8-12 weeks (± 7 days) until disease progression.

There will be a tumor assessment at End of Treatment (± 3 days) if the patient discontinues for any reason other than disease progression and the last tumor assessment has been performed > 21 days prior to this day. Subjects included in the Phase II part of the study, who discontinue study treatment due to another reason than disease progression, should be followed up monthly via a phone call and undergo tumor assessments every 8 weeks (± 7 days) until disease progression or initiation of subsequent anti-neoplastic therapy, or death, whichever occurs first ([Section 7.1.5.2](#)). Patients who have been on either dual- or triple-combination treatment for ≥ 24 months (Cycle 25 Day 1 onward) and then discontinue study treatment for any reason other than disease progression will have CT/MRI scans every 8-12 weeks (± 7 days).

At Screening/baseline the following should be performed:

- A CT scan with intravenous (i.v.) contrast of chest, abdomen and pelvis is required for all patients.
- In subjects with a history of asymptomatic brain metastases, a brain MRI or CT scan must be performed.

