10.4.2.2 Phase II

Efficacy will be assessed using the local CT/MRI assessments evaluated under RECIST version 1.1, [Appendix 1](#). The Best Overall Response (BOR) for each patient and individual lesion measurements will be listed. The (BOR) is the best response recorded from the start of the treatment until disease progression. Based on patients' BOR during study, the Objective Response Rate (ORR) and the Disease control Rate (DCR) are then calculated.

The ORR is defined as the proportion of patients with a best overall response of Complete Response (CR) or Partial Response (PR). The DCR is defined as CR or PR or Stable Disease (SD).

Patients who withdrew prematurely due to progression of disease without having any post-dose tumor assessment will be classified as treatment failures. Similarly, patients who died due to their disease without having any post-dose tumor assessment will be classified as treatment failures.

Arm 1 dual combination: patients with metastatic BRAF V600 mutant mCRC

A Bayesian design will be used in order to estimate the true DCR. Inferential statements will be based on the uncertainty of this quantity. For a Bayesian design it is required to specify a prior distribution for the parameter of interest, in this case DCR.

For the current study, the prior clinical assumption for a MEK inhibitor in BRAF V600 mutant mCRC at pre-specified dose-levels will be used in order to derive a minimally informative unimodal Beta prior distribution that reflects the level of uncertainty around the DCR before starting the current trial. At completion of the study, this prior distribution will be updated with all the data available in this part of the study.

Once updated, the distribution summarizes the probability that the true DCR at the dose of the LGX818 and MEK162 combination used in the Phase II lies in the following categories:

- [0, 20%) unacceptable efficacy
- [20%, 30%) limited efficacy
- [30%, 40%) moderate efficacy
- [40%, 100%] clinically relevant efficacy

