If the observed DCR is equal or greater than 30% (i.e. 9 or more patients with BOR of SD, PR or CR), then this will be considered as evidence of clinically relevant anti-tumor efficacy of the LGX818 and MEK162 combination in BRAF V600 mutant mCRC. Note that for a sample size of 28, if at least 9 patients with DCR are observed, then the true DCR has posterior risk of being in the unacceptable efficacy category of less than 10% ([Section 10.8](#)). If the observed DCR is less than 20% then inactivity will be declared.

A minimally informative Beta prior distribution of the true DCR is derived as follows: **a priori** it is assumed that the true mean of the DCR equals 30%. A true DCR of 30% is the midpoint between limited and moderate efficacy and serves as a compromise between a skeptical view assuming the treatment has only limited efficacy and an optimistic view assuming the treatment has moderate efficacy.

The parameters of the minimally informative Beta prior distribution of the DCR are then derived noting that $b = 1$ and $a/(a + b) = 0.30$ i.e. $a = 0.428$ and $b = 1$

Arm 2 dual combination: patients with metastatic BRAF V600 mutant melanoma who have progressed after prior treatment with selective BRAF inhibitor

A Bayesian design will be used in order to estimate the true ORR. Inferential statements will be based on the uncertainty of this quantity. For a Bayesian design it is required to specify a prior distribution for the parameter of interest, in this case ORR:

For the current study, the prior clinical assumption for a MEK inhibitor in BRAF V600 mutant melanoma at pre-specified dose-levels will be used in order to derive a minimally informative unimodal Beta prior distribution that reflects the level of uncertainty around the ORR before starting the current trial. At completion of the study, this prior distribution will be updated with all the data available in this part of the study.

Once updated, the distribution summarizes the probability that the true ORR at the dose of the LGX818 and MEK162 combination used in the Phase II lies in the following categories:

- [0, 10%) unacceptable efficacy
- [10%,15%) limited efficacy
- [15%, 20%) moderate efficacy
- [20%, 100%] clinically relevant efficacy

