10.7 Interim analysis

An interim analysis for futility will be performed in the phase II BRAF V600 mutant mCRC arm (dual-combination arm 1), when 14 patients (50% of the total sample size) have completed 4 cycles of treatment. As mentioned in Section 10.8, study results are successful if 9 responses are observed at the end of the trial. At the interim analysis, if the predictive probability of success is < 13%, i.e. if less than 3 responses (DCR at week 16) are observed, this study arm will be stopped for futility.

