- PR = at least two determinations of PR or better at least 4 weeks apart before progression (and not qualifying for a CR) where confirmation required or one determination of PR prior to progression where confirmation not required

- SD = at least one SD assessment (or better) > 6 weeks after randomization/start of treatment (and not qualifying for CR or PR).

The protocol should state if randomization or start of treatment is used as start date (baseline). This is then used in all definitions.

If a different minimum follow-up period is required to classify for overall response= 'stable disease', this must be specified in the protocol.

- PD = progression ≤ 12 weeks after randomization/ start of treatment (and not qualifying for CR, PR or SD).

If PD in a different follow-up period is considered overall response='progressive disease', this must be specified in the protocol.

The protocol should state if discontinuation due to 'Disease progression' or death due to study indication is considered PD even if this was not accompanied by documentation of PD based on tumor measurements. This depends on Phase of the study and the primary endpoint (e.g. Phase III studies in which progression-free survival is primary endpoint should consider only documented PD, whereas Phase I and II studies may consider all clinical deteriorations PD). The following sentence therefore is only applicable if this is specified in the protocol:

- Patients with symptoms of rapidly progressing disease without radiologic evidence will be classified as progression only when clear evidence of clinical deterioration is documented and/or patient discontinued due to 'Disease progression' or death due to study indication.
- UNK = all other cases (i.e. not qualifying for confirmed CR or PR and without SD after more than 6 weeks or early progression within the first 12 weeks)

Overall lesion responses of CR must stay the same until progression sets in, with the exception of a UNK status. A patient who had a CR cannot subsequently have a lower status other than a PD, e.g. PR or SD, as this would imply a progression based on one or more lesions reappearing, in which case the status would become a PD.

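### Arm 1's primary endpoint is named as disease control at week 16 but defined and decided on best overall response, so interim and final analyses can count different events and the stated error rates have no fixed endpoint

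*Protocol*

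**What the plan says.** Section 10.4.1 gives the arm 1 variable as follows: "the primary variable is the Disease Control Rate (DCR) at week 16. DCR is defined as the proportion of patients with a best overall response". Qualifying responses are CR, PR and SD. Section 10.4.2.2 describes BOR as the "best response recorded from the start of the treatment until disease progression", with no reference to week 16, and sets the success criterion on that scale: "i.e. 9 or more patients with BOR of SD, PR or CR", out of 28. Section 10.8 computes its error rates by counting patients with SD or better, also without a time point. Table 3-1 says only DCR per RECIST v1.1.

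Week 16 reappears in section 10.7, where the interim is taken after 14 patients have completed four 28-day cycles: "if less than 3 responses (DCR at week 16) are observed, this study arm will be stopped for futility". That section ties the rule to a predictive probability of success below 13%, where success is 9 responses at the end.

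Appendix 1, section 14.1.17, supplies the duration rule: "SD = at least one SD assessment (or better) > 6 weeks after randomization/start of treatment". It adds: "If a different minimum follow-up period is required to classify for overall response= 'stable disease', this must be specified in the protocol". The protocol states no other minimum. Under section 7.2.1, Phase II scans fall at the end of "Cycle 2 and then every 8 weeks (2 cycles) thereafter during the study treatment until disease progression", that is, at weeks 8 and 16, each within 7 days.

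**The concern.** Disease control at week 16 and BOR-based disease control are different events. With scans at weeks 8 and 16, SD at week 8 followed by PD at week 16 satisfies the BOR rule and fails the week-16 rule. Two analysts could follow this protocol, use the same scans and report different primary results for arm 1.

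Two things are at stake. First, the interim may count one event and the final another. The predictive probability behind the stopping rule is meaningful only if both count the same event; otherwise the arm could stop on week-16 control while its BOR count was on course for 9. Second, the bounds of 20% (unacceptable) and 40% (clinically relevant) carry the error rates in section 10.8. The same percentage is a stricter or a more lenient requirement depending on which event it describes.

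**Working it through.** **Inputs.** n = 28, success at 9 or more, rates 20% and 40% (sections 10.4.2.2 and 10.8); prior Beta(0.428, 1) (section 10.4.2.2); interim at 14 patients, stop if fewer than 3 (section 10.7). The share of week-8 control lost by week 16 is not in the document and is assumed below.

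**Step 1: reproduce the plan's figures, with one endpoint throughout.**
- P(X ≥ 9 | n = 28, p = 0.20) = 0.0900 (stated 9.0%).
- P(X ≥ 9 | n = 28, p = 0.40) = 0.8515 (stated 85.2%).
- Posterior after 9 of 28 is Beta(0.428 + 9, 1 + 19) = Beta(9.428, 20); P(DCR < 0.20) = 0.0700 (stated 7.0%).
- Beta-binomial predictive probability of reaching 9 of 28: 2.5% after 2 of 14 and 13.4% after 3 of 14. This agrees with stopping below 3 at a 13% threshold, and the calculation treats interim and final counts as the same event.
- Power at 40% with the interim: 84.1% (stated 82.3%), a difference that does not affect this point.

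**Step 2: the mixed reading.** Suppose the true week-16 rate is 20% and success is counted on BOR. Every patient controlled at week 16 is also a BOR success. If a share L of week-8 control is lost by week 16, the BOR rate is p_B = 0.20 / (1 − L), and the chance of declaring activity is P(X ≥ 9 | 28, p_B).

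For the version with the interim, let x of the first 14 be BOR successes, with x ~ Bin(14, p_B). Let y of those be controlled at week 16, with y ~ Bin(x, 0.20 / p_B). The arm continues if y ≥ 3 and succeeds if the second 14 patients supply at least 9 − x more. The chance of stopping is P(Y ≤ 2 | 14, 0.20) = 44.8% in every row.

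| Assumed L | p_B | P(≥ 9 of 28), no interim | With week-16 interim |
|---|---|---|---|
| 10% | 22.2% | 15% | 14% |
| 20% | 25.0% | 25% | 21% |
| 30% | 28.6% | 41% | 31% |
| 40% | 33.3% | 62% | 43% |
| 50% | 40.0% | 85% | 51% |
| Constant hazard, p_B = √0.20 | 44.7% | 94% | 54% |

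**Step 3: the opposite case.** Suppose 40% is a BOR rate and success is counted at week 16. The week-16 rate is 0.40 × (1 − L), which is 36% at L = 10% and 20% at L = 50%. P(X ≥ 9 | 28) falls from 85.2% to 73% and 9% respectively.

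**The case against.** The best defence is that the 9.0% is stated conditionally on a true DCR of 20%, and DCR is defined by BOR in section 10.4.1 and in Appendix 1. On that reading the rates, the success rule and the error rates are one coherent set, and the words about week 16 are a loose label. Section 10.7 could likewise mean BOR assessed by the time four cycles are complete, or week 16 could be an intended minimum duration for SD. The first part stands: no figure in section 10.8 is miscalculated. The rest shows that the text admits several readings, not that it settles on one. Appendix 1 requires any other SD minimum to be stated, and none is.

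A reader might go further and infer that the 9% false-positive rate is destroyed and that arm 1 would almost always be declared active, citing 94% at a true week-16 rate of 20% and 55% at 10%. The documents do not support that. It presumes that 20% is a week-16 benchmark, which is nowhere stated. It rests on a single assumed hazard. It also omits the week-16 interim, which on the same assumptions reduces those figures to 54% and 12%.

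A reader might also infer that the point-in-time definition is the only correct repair. It is one option, and step 3 shows that it would cost power if 20% and 40% were meant as BOR rates.

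**Conclusion.** The contradiction stands and should be resolved, because arm 1's primary conclusion depends on the reading taken. Sections 10.4.1 and 10.7 name week 16; the definition, the final decision rule and the Appendix 1 default use BOR.

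The 9.0% and 85.2% are valid only for the endpoint to which 20% and 40% belong, and the protocol leaves that open. If 20% is a week-16 rate while success is counted on BOR, any loss of control between the two scans raises the false-positive rate above 9.0%. That direction follows from the definitions. The size (15% to 85% for losses of 10% to 50%, or 14% to 51% with the interim) rests on assumed loss rates. If 20% is a BOR rate and success is counted on BOR, the final-analysis figures are unaffected, and what remains is the interim rule and the label.

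**What to change.** State one definition and use it in Table 3-1 and sections 10.4.1, 10.4.2.2, 10.7 and 10.8. Either of these would do:
- CR, PR or SD at the week-16 scan with no earlier PD, counting a patient without an evaluable week-16 assessment as a failure; or
- BOR of CR, PR or SD with an explicitly stated minimum duration for SD.

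Apply the chosen definition at both interim and final, say that the 20%, 30% and 40% bounds refer to it, and report the other version as supportive. The sample size of 28 and the cut-off of 9 can stay if the 20% and 40% rates are confirmed for that endpoint; otherwise restate the error rates.

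The cost is wording, plus a recalculation if the rates belong to the other endpoint. No new scans are needed. The reported DCR or the power may look less favourable. Because enrolment has closed and the study is open-label, the choice should be justified from the design intent behind the 20% and 40% rates, and both versions should be shown.
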